13.2.2 Recording and reporting protocol deviations and violations

Protocol deviations will be recorded in a protocol deviation log and logs will be submitted to the sponsors every 3 months. Each protocol violation will be reported to the sponsor within 3 days of becoming aware of the violation. All protocol deviation logs and violation forms should be emailed to [contact]. Protocol deviations of particular interest will also be recorded on the study database.

13.3 SERIOUS BREACH REQUIREMENTS

A serious breach is a breach which is likely to effect to a significant degree:

- (a) the safety or physical or mental integrity of the participants of the trial; or
- (b) the scientific value of the trial.

If a potential serious breach is identified by the Chief investigator, Principal Investigator or delegates, the co-sponsors ([contact]) must be notified within 24 hours. It is the responsibility of the co-sponsors to assess the impact of the breach on the scientific value of the trial, to determine whether the incident constitutes a serious breach and report to research ethics committees as necessary.

13.4 STUDY RECORD RETENTION

All study documentation will be kept for a minimum of 3 years from the protocol defined end of study point. When the minimum retention period has elapsed, study documentation will not be destroyed without permission from the sponsor.

13.5 END OF STUDY

The end of study is defined as the last participant's last visit.

The Investigators or the co-sponsor(s) have the right at any time to terminate the study for clinical or administrative reasons.

The end of the study will be reported to the REC, and R+D Office(s) and co-sponsors within 90 days, or 15 days if the study is terminated prematurely. The Investigators will inform participants of the premature study closure and ensure that the appropriate follow up is arranged for all

IRAS 299977/308830

Version 5.0 26Jun2024

participants involved. End of study notification will be reported to the co-sponsors via email to [contact]

A summary report of the study will be provided to the REC within 1 year of the end of the study.

13.6 INSURANCE AND INDEMNITY

The co-sponsors are responsible for ensuring proper provision has been made for insurance or indemnity to cover their liability and the liability of the Chief Investigator and staff.

The following arrangements are in place to fulfil the co-sponsors' responsibilities:

- The Protocol has been designed by the Chief Investigator and researchers employed by the University and collaborators. The University has insurance in place (which includes no-fault compensation) for negligent harm caused by poor protocol design by the Chief Investigator and researchers employed by the University.
- Sites participating in the study will be liable for clinical negligence and other negligent harm to individuals taking part in the study and covered by the duty of care owed to them by the sites concerned. The co-sponsors require individual sites participating in the study to arrange for their own insurance or indemnity in respect of these liabilities.
- Sites which are part of the United Kingdom's National Health Service will have the benefit of NHS Indemnity.
- Sites out with the United Kingdom will be responsible for arranging their own indemnity or insurance for their participation in the study, as well as for compliance with local law applicable to their participation in the study.

14 REPORTING, PUBLICATIONS AND NOTIFICATION OF RESULTS

14.1 AUTHORSHIP POLICY

Ownership of the data arising from this study will reside with the study team.

14.1.1 Reporting and publication

Results of the trial will be posted on the ISRCTN registered clinical trial website. The trial Chief Investigator and co-investigators will oversee decisions around presentation of results to scientific and clinical meetings, public/press releases, and social media notifications. The trial data will be published in peer-reviewed journals. The decisions surrounding publication will be made by the Chief Investigator and co-investigator.

14.1.2 Data Sharing

Consent will be sought from participants to permit sharing of anonymised data with funders and collaborators or published on publicly available resources as appropriate.

Co-investigators will have the right to access the final data set for the purpose of additional analyses that are consistent with the consent provided by participants.

CR007-T02 v0.5 Page **54** of **69**

IRAS 299977/308830

Version 5.0 26Jun2024

Following publication of the primary paper, a de-identified individual participant data set will be submitted to a data archive for sharing purposes. Access to this data set will be under a controlled access model in line with ECTU policies at that time.

CR007-T02 v0.5 Page **55** of **69**

IRAS 299977/308830

Version 5.0 26Jun2024

16 APPENDIX A DEFINITION OF COMPLICATIONS

16.1 Assessment of Complications

All postoperative complications will classified using the Hip Fracture Postoperative Morbidity Survey (38):

Morbidity type	Criteria definition: Presence of one or more of the following:
Pulmonary	The patient developed a new requirement for oxygen or respiratory support;
Infectious	Currently on IV antibiotics;
	Has had a temperature of >38@C in the last 24hr;
	*Has a white cell count level requiring in hospital review or treatment;
Renal	Presence of oliguria <500 mL/24 hr;
	Increased serum creatinine (>30% from preoperative level);
	New urinary catheter in situ;
Gastrointestinal	Unable to tolerate an enteral diet for any reason including nausea, vomiting, and abdominal distension (use of antiemetic); *Diarrhoea
	*New poor appetite causing poor oral intake
Cardiovascular	Diagnostic tests or therapy within the last 24 hr for any of the following: (1) new MI or ischemia, (2) hypotension (requiring fluid therapy >200 ml/hr or pharmacological therapy), (3) *dizziness - significant postural hypotension on sitting or standing up (4) cardiac arrhythmia that requires treatment or further investigation, (5) pulmonary oedema, (6) thrombotic event (requiring anticoagulation).
Neurological	New focal neurological deficit, confusion/ delirium, coma.
Haematology	Requirements for any of the following within the last 24 hr: packed erythrocytes, platelets, fresh-frozen plasma, or cryoprecipitate.
Wound	Wound dehiscence requiring surgical exploration or drainage of pus from the operation wound with or without isolation of organism; *Leaky wound requiring frequent dressing change
Pain	New and/or exacerbated postoperative pain significant enough to require any of the following: parenteral OR *oral opiates and/or continuing of additional analgesia; *pain limiting sitting up in bed or out on the chair.
*Endocrinology	*Difficult to control diabetes- hypoglycaemia or hyperglycaemia that requires specialist input
*Assisted	*A new or escalated postoperative requirement for mobility assistance with two people and a walking aids;
Ambulation	*Fatigue quickly limiting mobility.
*Psychological	*A new or exacerbated postoperative anxiety affecting mobility and /or self-care (coping at home).

Abbreviations: WCC, white cell count, IV, intravenous, MI, myocardial infarction, * New domains and criteria definitions.

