1.4.2 Secondary Endpoints

Secondary outcomes at 30 days are as follows:

- 1. All-cause mortality
- 2. New Myocardial Injury post-randomisation (New MINS)
- 3. Individual MACE components (including type of arrhythmia)
- 4. Complications (including AKI, infection, delirium)
- 5. Proportion of participants transfused; volume of blood transfused per patient
- 6. Discharge destination (home, other hospital, nursing home, other)
- 7. Acute hospital length of stay
- 8. ED-5D-5L

Additional secondary outcomes at 120 days are as follows:

- 1. All cause mortality
- 2. Secondary care costs
- 3. Unplanned hospital readmissions
- 4. Mobility (as defined by NHFD or SHFA dataset
- 5. Residential status (as defined by NHFD or SHFA dataset)
- 6. EQ-5D-5L
- 7. Health services resource use

Clinical outcomes will be measured until acute hospital discharge or 30 days post randomisation whichever is soonest. Death, readmission, mobility, residential status, quality of life and resource use will be measured at 120 days post-randomisation.

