5.2 STUDY INTERVENTION

5.2.1 Blood Transfusion

Once participants are randomised, the transfusion laboratory at the site will be informed of their treatment allocation by the research team. Where possible the blood transfusion laboratory will add a 'flag' to the participants record to ensure that the treatment arm is recorded, and that blood is released according to the patient's study group. Currently red blood cell transfusions are ordered and released using a combination of paper and electronic requests and this will need to be tailored according to the individual site's processes.

Intervention: liberal transfusion protocol

Participants randomised to the liberal arm will receive one unit of red blood cells as soon as possible after randomisation (ideally within 24 hours) to keep their haemoglobin within the range of 90-110 g. L⁻¹. Participants should receive any subsequent transfusions within 24 hours of an Hb of 90 g.L⁻¹ or less. Transfusions that do not occur or occur > 48 hours post-randomisation will be considered a protocol deviation as detailed in section 13.2.

Comparator: restrictive transfusion protocol

Participants randomised to the restrictive arm will not receive a blood transfusion until their haemoglobin falls to 75 g.L⁻¹ or less and the aim will be to keep their haemoglobin within the range 75-90 g.L⁻¹. Participants should receive a blood transfusion within 24 hours of an Hb of 75 g.L⁻¹ or less. Transfusions that do not occur or occur >48 hours after an Hb of 75 g.L⁻¹ or less will be considered a protocol deviation as detailed in section 13.2.

In all participants these targets apply for the duration of acute hospital admission or 30 days post-randomisation whichever is soonest. Single units of red blood cells will be given, and the haemoglobin rechecked before a further transfusion, unless the responsible clinician decides that multiple red blood cell units are indicated. Situations may arise where a participant has a further haemoglobin measurement **after** the threshold Hb measurement , but **before** a transfusion is given, which alters the requirement to transfuse. In this case, clinicians should use the most recent Hb measurement to determine whether a transfusion is required, the aim being to follow the protocol as closely as possible to keep participants in their allocated Hb range of restricted or liberal.

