- G number as a record of all red cell transfusions administered
- AKI (KDIGO criteria) (from review of paper and electronic case notes)
- Delirium (via 4AT) twice in days 1 5 following randomisation (supplemented by review of paper and electronic case notes)
- All post-operative complications using Hip Fracture Post-Operative Morbidity Survey (Appendix A)
- Episodes of chest pain days 0 3

At 30 days post randomisation the following will be collected:

- G number as a record of all red cell transfusions administered
- length of hospital stay
- Major adverse cardiac events (MACE) including myocardial infarction (from review of paper and electronic case notes
- New MINS
- Copy of any non-trial cardiac investigations carried out locally e.g. angiogram, echocardiograph uploaded to CRF
- New stroke*
- New pulmonary embolus*
- All complications (Appendix A)
- AKI using KDIGO definitions

IRAS 299977/308830

Version 5.0 26Jun2024

- Mortality
- EQ-5D-5L
- Health services utilisation (HE questionnaire)

At 120 days post randomisation the following will be collected:

- Acute hospital discharge destination
- Emergency readmission
- Readmission specialty and location
- Mortality
- Cause of death (if applicable)
- Re-operation
- Total number of hospital, ICU, HDU bed days.
- Place of residence (using NHFD)
- Mobility (using NHFD)
- EQ-5D-5L
- Health services utilisation (HE Questionnaire)

*Definition of stroke or pulmonary embolus is "confirmation by the clinical team that the patient has had a stroke or pulmonary embolus".

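### The complications survey scores red-cell transfusion as a complication, so the Haematology domain, and any overall complication measure that includes it, is tilted against the liberal arm by definition

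*Protocol*

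**What the plan says.** Section 1.4.2 lists, as 30-day secondary outcome 4, "Complications (including AKI, infection, delirium"). Outcome 5 in the same list is the proportion transfused and the volume given.

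Appendix A, 16.1, supplies the instrument: "All postoperative complications will classified using the Hip Fracture Postoperative Morbidity Survey". The heading of the criteria column sets the scoring rule for each domain: "Criteria definition: Presence of one or more of the following". The Haematology row reads "Requirements for any of the following within the last 24 hr: packed erythrocytes, platelets, fresh-frozen plasma, or cryoprecipitate". No footnote or other section exempts transfusions given under the trial's own strategy.

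Section 7.1 collects the survey after randomisation, and again lists "All complications (Appendix A") at day 30, with no domain left out.

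Section 5.2.1 sets the two strategies. "Participants randomised to the liberal arm will receive one unit of red blood cells as soon as possible after" randomisation, preferably within a day. "Participants randomised to the restrictive arm will not receive a blood transfusion until their" haemoglobin has fallen to 75 g/L or less.

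**The concern.** Everyone is randomised at a haemoglobin of 90 g/L or less. Take two participants in the same clinical state at, say, 85 g/L. The liberal one is due a unit and so meets the Haematology criterion; the restrictive one is not due a unit and does not. Nothing about their course differs except the allocation.

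The trial weighs possible cardiac benefit of a liberal strategy against possible harm from transfusion. A complications outcome with a built-in excess in the liberal arm would bear directly on that judgement, and a reader of the results table could not separate the artefact from real harm. How the domains are analysed can be left to the statistical analysis plan. The definition itself is fixed in the protocol, and an analysis faithful to Appendix A would inherit the problem.

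**Working it through.** The protocol gives no figure for this outcome, so there is nothing to reproduce. The check has two parts.

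**Reading the sections together**

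1. 16.1: any one criterion makes a domain positive, and needing packed red cells within the past 24 hours is such a criterion.
2. 5.2.1: at the same haemoglobin, a reading that triggers transfusion in the restrictive arm also triggers it in the liberal arm. Readings above 75 and up to 90 g/L trigger it in the liberal arm only.
3. 7.1: the survey is completed after randomisation, so allocation can act on it.
4. 1.4.2: red-cell use is already outcome 5, so the criterion adds no information on red cells.

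It follows that the domain favours the restrictive arm with no true effect on any complication.

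**Illustration of size**

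Let h be the share of an arm scoring the Haematology domain and b the share with at least one other domain, taken as equal in both arms (no true effect) and independent of h. Then

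- P(any domain) = 1 − (1 − b)(1 − h)
- difference between arms = (1 − b)(h_lib − h_res)

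Assumed inputs: h_lib 0.81 to 1.00, h_res 0.20 to 0.50, b 0.30 to 0.90. None of these is given by the protocol for this purpose. The 0.81 borrows the pilot's liberal-arm compliance (1.1.4) only as a convenient low value.

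| b | h_lib | h_res | Liberal | Restrictive | Difference |
|---|---|---|---|---|---|
| 0.30 | 1.00 | 0.20 | 1 − 0.7×0 = 100% | 1 − 0.7×0.8 = 44% | 56 points |
| 0.50 | 0.90 | 0.30 | 1 − 0.5×0.1 = 95% | 1 − 0.5×0.7 = 65% | 30 points |
| 0.90 | 0.81 | 0.50 | 1 − 0.1×0.19 = 98.1% | 1 − 0.1×0.5 = 95.0% | 3.1 points |

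With the 507 per arm of section 9.1 and a two-sided 5% test of two proportions, the chance of a significant result against the liberal arm is about 77% in the last row. It is about 95% or more in every other combination tried, although no true effect was assumed.

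These inputs treat every transfused participant as caught by the 24-hour look-back. If only a fraction w of them were surveyed in time in each arm, both h values and the difference would shrink by w. With w = 0.5, for example, the last row becomes 0.1 × 0.5 × 0.31, or about 1.6 points. The table is therefore not a lower bound.

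If the domain is left out, the allocation-driven part of the difference is zero by construction.

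**The case against.** The strongest reply is that the protocol nowhere specifies an any-complication rate, a domain count or a total score. If each domain is reported separately, the artefact stays in the Haematology row, which then repeats outcome 5, and few readers would take more transfusion in a liberal-threshold arm as harm. The complications that matter most have their own definitions: cardiac events (16.2), acute kidney injury by KDIGO (16.3) and delirium by 4AT (16.4). This limits the reach of the point. It does not remove it, because 16.1 still presents the allocated treatment as a complication and nothing prevents an aggregate that includes it.

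The size is also open to challenge. Restrictive participants transfused at their own threshold score too. Section 2.3 allows randomisation before surgery, and a preoperative unit is not obviously a postoperative complication. Other domains may be very common, since postoperative pain needing opiates or a new urinary catheter is enough to score; a large b pushes the any-complication difference towards the small end. All of this stands.

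Three stronger readings are tempting, but the documents do not support them:

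- **A gap of roughly 30 to 80 points in the Haematology domain.** It is only h_lib − h_res under the assumed inputs (0.81 − 0.50 to 1.00 − 0.20). The pilot's 81% and 64% are overall protocol compliance, not shares transfused; the pilot's restrictive trigger was 70 g/L; and the gap ignores the look-back.
- **A distorted infection outcome, because fever alone scores the Infectious domain and febrile reactions are expected.** Appendix B gives no frequency. Discounting fever after transfusion would apply mostly to the liberal arm and would itself depend on allocation.
- **A distorted cost-consequence analysis.** Section 9.3 lists EQ-5D-5L scores, resource use and costs, not survey scores. Extra red-cell use there is a real resource difference.

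**Conclusion.** The point holds as a fault in an outcome definition. As written, Appendix A scores the liberal strategy as a complication, and the Haematology domain, with any rate or count that includes it, is tilted against the liberal arm without any true effect.

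The documents do not determine the size. Under the stated assumptions an any-complication rate could differ by about 3 to 56 percentage points, and by less if survey days fall more than 24 hours after most transfusions. The adjudicated primary outcome, mortality, KDIGO acute kidney injury and 4AT delirium are not affected.

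**What to change.** State in Appendix A, 16.1, that red-cell transfusion does not count as a complication in this trial. The simplest way is to exclude the Haematology domain from every between-arm complication comparison and count. If the case report form records the blood components separately, packed red cells can be dropped and the rest of the domain kept; the protocol does not show whether it does. Report red-cell use only under 30-day secondary outcome 5. Carry the same wording into the statistical analysis plan.

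The change is one sentence and alters nothing in clinical management. Exclusion needs no new data, since section 7.1 already records units, volume and each red-cell transfusion. The cost is that any total would no longer match the full survey as listed, and excluding the whole domain also drops platelets, plasma and cryoprecipitate from complication counts.

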16.2 Assessment of Cardiac Complications

Myocardial infarction: Any cardiac ischaemic event fulfilling 4th Universal Definitions for Myocardial Infarction

Myocardial Injury after Non-Cardiac Surgery: Troponin elevation above the assay upper reference limit within 30 days of randomisation which does not satisfy universal definitions for myocardial infarction.

Arrhythmia: ECG evidence of rhythm disturbance resulting in a fall in mean arterial pressure of greater than 20% or requiring treatment (anti-arrhythmic agents, vasoactive agents, intra venous fluid, etc.).

Cardiac or respiratory arrest: As per UK Resuscitation Council Guidelines.

Cardiogenic pulmonary oedema: Appropriate clinical history and examination with consistent chest radiograph.

Pulmonary embolism: Computed tomography (CT) pulmonary angiogram, clinical or echocardiographic evidence with appropriate clinical history.

CR007-T02 v0.5 Page **59** of **69**

IRAS 299977/308830

Version 5.0 26Jun2024

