1.1.4 Pilot Study Results

Our group have undertaken a single centre pilot RCT in 200 people exploring the effect of restrictive versus liberal transfusion practice on cardiac injury following surgery for hip fracture (Clinical trials NCT03407573).(11)

This demonstrated the following key findings in the UK hip fracture population:

- the mortality at 30 days in this group is 6-7%
- the rate of co-existing cardiovascular disease is over 60%.
- the transfusion rate in this group is approximately 30%.
- the incidence of *clinically diagnosed* cardiac complications following hip fracture surgery in anaemic people is 14%.
- the incidence of MINS (perioperative elevated troponin) in anaemic people following hip fracture surgery is over 60%.

Our pilot study concluded that a trial of restrictive versus liberal transfusion practice was feasible but that transfusion before reaching the trigger of 70 g.L⁻¹ in the restrictive group was the leading cause of protocol deviation. Overall protocol compliance was 64% in the restrictive group and 81% in the liberal group suggesting that many clinicians would prefer to transfuse at a higher Hb target than 70 g L^{-1,} consistent with the variation in national and international guidance.

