1.4 ENDPOINTS

1.4.1 Primary Endpoint

The primary outcome will be death OR major adverse cardiac events (MACE) OR new myocardial injury after non cardiac surgery (new MINS) within 30 days of randomisation.

MACE will be defined as any combination of the following:

- Myocardial Infarction: Diagnosed using the 4th Universal Definitions for MI(14)
- New Arrhythmia: ECG confirmed arrhythmia resulting in a fall in mean arterial pressure of >20% and requiring pharmacological or cardioversion treatment.
- Cardiac or respiratory arrest: Resuscitation Council UK definitions
- Cardiogenic pulmonary oedema.

New MINS will be defined as : new elevated postoperative troponin above the upper reference limit (URL) with a rise/fall pattern indicative of acute myocardial injury occurring in the first 30 days (and typically within 72 h) after surgery; attributable to a presumed ischemic mechanism,

IRAS 299977/308830

Version 5.0 26Jun2024

clinical symptoms masked by sedation or analgesia in the perioperative setting, ischemic features (e.g. ECG, echocardiographic changes) not required.

To maximize validity and consistency, all participants will have troponin measured at randomisation (baseline), and then twice more in days 1 to 5, ideally on the 1st and 3rd calendar days after randomisation with all samples being at least 24h apart from each other, and 12-lead ECGs will be performed at baseline and repeated once in days 2 - 5. The primary outcome will be determined by an expert adjudication team blinded from group allocation.

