2.3 DURATION OF PARTICIPANT INVOLVEMENT

[figure not shown]
We will screen people with hip fracture who meet the age inclusion criteria. This can take place from the time the patient enters the hospital and up to and including 7 days post –surgery. Once potential participants have been identified they will be followed daily to check the haemoglobin level measured on their blood results. If a haemoglobin measurement triggers inclusion in the study, that is, if the Hb falls to 90 g.L⁻¹ or less, then the patient will be randomised. Randomisation should take place as soon as possible after the triggering haemoglobin measurement and no later than post-operative day 8. This can occur pre-operatively or postoperatively whenever on the patient journey that the Hb value first falls to 90 g.L⁻¹ or less.

Participants who are randomised in the study follow one of two arms: restrictive or liberal blood transfusion. Both arms have the same measurements, data collection and follow up. The participants will be in the study for up to 120 days from entry. Participants will be sent a summary of the study results at the end of the trial by the University of Edinburgh if permission is given to do so. Thereafter there will be no further participant-researcher interactions.

IRAS 299977/308830

Version 5.0 26Jun2024

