9 STATISTICS AND DATA ANALYSIS

9.1 SAMPLE SIZE CALCULATION

Sample size calculations were informed by our pilot studies, the 2019 NHFD Annual Report, the FOCUS trial (US-based pre-2010), other observational studies and expert opinion. In people with hip fracture, we estimate 30-day all-cause mortality will be 7%, rates of MACE will be 10% and rates of new MINS will be 20%. Note these rates reflect 'whole population' outcome rates and are expected to underestimate rates seen in the proposed trial population (enriched by anaemia status which is associated with higher death and MACE event rates).

Rates of cardiac injury and death in anaemic participants are likely to be higher (as in our pilot trial), and components will occur concurrently in some participants. Conversely, routine Troponin/ECG measurement may increase MI detection compared to previous studies. Overall, we estimate a population 'usual care' MACE rate (including death) of 10% at 30 days. We estimate the rate of new MINS in this population to be 20% based on pilot data. Based on clinical consensus among UK opinion-leaders/experts, we consider an absolute risk reduction (ARR) of 5% in the primary outcome to be a realistic meaningful effect size that would change practice (33% Relative RR). Importantly, this would represent a number needed to treat (NNT) of 20 for every patient receiving liberal transfusion to avoid a death and/or MACE outcome compared to the restrictive group.

We recognise limitations of a composite primary outcome treated as a binary (yes/no) indicator, because components treated equally may have differing importance to patients and clinicians. Importantly, nonfatal and/or less severe parts of the composite may occur more frequently and might dominate overall event rates. We will address this with an ordinal ranking of the possible outcomes at 30 days (1 best; 6 worst) according to severity/importance:

CR007-T02 v0.5 Page **41** of **69**

IRAS 299977/308830

Version 5.0 26Jun2024

[1] No death, no MACE, no new MINS
[2] No death, no MACE, but new MINS.
[3] No Death ≥1 MACE
[4] Death, no MACE, no new MINS;
[5] Death, plus new MINS
[6] Death plus ≥1 MACE.

We will also report rates of MACE components and new MINS separately.

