Thus the assumed 30 day mortality rate is 7%, MACE at 30 days is 10%, and rate of new MINS is 20%. To detect a 30% RRR (corresponding to a log-odds-ratio of approximately 0.64) and assuming proportional odds (34) between the liberal and restrictive groups, we require a sample size of 507 participants in each arm, using a Wilcoxon-Mann-Whitney rank-sum test with a 5% two-sided significance level and 90% power. Allowing for a 10% dropout rate, we propose to recruit 563 participants per group. Total sample size 1126 participants.

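### New MINS, the largest assumed component of the primary outcome, is defined inconsistently, and no section ties it to the troponin measured at randomisation

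*Protocol*

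**What the plan says.** Three places in the protocol describe the event.

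- **Section 1.4.1 (Primary Endpoint)** gives this definition of new MINS: "new elevated postoperative troponin above the upper reference limit (URL) with a rise/fall pattern indicative of acute myocardial injury occurring in the first 30 days". It counts from surgery and requires a presumed ischaemic mechanism.
- **Section 1.4.2 (Secondary Endpoints)** lists "New Myocardial Injury post-randomisation (New MINS"). It gives no threshold or pattern, but the reference point is randomisation.
- **Appendix A, section 16.2**, defines MINS as "Troponin elevation above the assay upper reference limit within 30 days of randomisation which does not satisfy universal definitions for myocardial infarction". It asks for no newness, no rise or fall, and no cause.

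Four other places bear on how these are read.

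- Section 2.3, on when randomisation happens once the trigger haemoglobin is reached: "This can occur pre-operatively or postoperatively whenever on the patient journey that the Hb value first falls".
- Section 5.2.2 has the baseline troponin taken after randomisation, on the same day and ideally within 4 hours.
- Section 1.3.2 lists myocardial injury (any troponin release above the upper reference limit, URL) as a secondary outcome separate from new MINS. Section 1.4.2 has only one entry.
- Section 6.3 gives three URLs for the assay: 26 ng/L overall, 16 for females and 34 for males. It does not say which applies to the endpoint.

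Sections 9.1 and 9.2 use new MINS to separate rank 1 from rank 2, and rank 4 from rank 5.

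**The concern.** An outcome of a randomised comparison should be an event that happens after allocation. Under the Appendix A wording, a patient whose troponin was already above the URL at the baseline draw, and who has no MI, counts as having MINS whatever happens next. This need not be rare. Section 1.1.2 says haemoglobin usually falls to the trigger within three days of surgery, and section 1.4.1 says MINS typically occurs within 72 hours of surgery, so injury and randomisation fall in the same few days.

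The two rates in the protocol show how much the definition could matter. Section 9.1 plans on 20% new MINS. Section 1.1.4 reports that in the pilot the incidence of MINS ("perioperative elevated troponin) in anaemic people following hip fracture surgery is over 60"%).

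At stake are consistent ranking by the blinded adjudicators, whether rank 2 measures something transfusion could affect, and whether the 20% planning rate describes the event that will be counted.

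**Working it through.** **1. The definitions applied to the same patients** (no MI, no other MACE, alive at 30 days)

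| Patient | 1.4.1 | 1.4.2 | Appendix A 16.2 |
|---|---|---|---|
| Randomised after surgery; baseline at or below URL; later rise above it, presumed ischaemic | met | met | met |
| Randomised after surgery; baseline above URL; later values flat | not met | not met | met |
| Randomised after surgery; baseline above URL; later values falling | arguable: a fall is present, and what it must be new against is not stated | not met | met |
| Randomised before surgery; rise above URL before the operation | not met: not postoperative | met | met on its criterion |

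Only the first patient is ranked the same way under all three. Rows 2 and 3 can admit injury from before allocation; row 4 can omit injury after it.

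**2. The planned sample size**

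Inputs from section 9.1: "Thus the assumed 30 day mortality rate is 7%, MACE at 30 days is 10%, and rate of new MINS is 20"%; "we estimate a population 'usual care' MACE rate (including death) of 10% at 30 days"; a 30% relative risk reduction (RRR); "using a Wilcoxon-Mann-Whitney rank-sum test with a 5% two-sided significance level and 90% power"; 507 per arm.

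Because the 10% MACE rate includes death, non-fatal MACE is 10 − 7 = 3%. The control distribution is then 70% no event, 20% MINS, 3% non-fatal MACE and 7% death. I split death evenly over ranks 4 to 6; this is an assumption and hardly affects the result. A 30% reduction in each component gives 79/14/2.1/4.9% in the treated arm.

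Let θ = P(treated better) + ½P(tie), and V = 1 − Σp̄³ with p̄ the mean rank proportions of the two arms.

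- n per arm = (1.960 + 1.282)² V / [6(θ − ½)²]
- θ = 0.545, V = 0.5816
- n = 10.507 × 0.5816 / (6 × 0.045²) = 503, within 1% of the stated 507
- Power at 507 = Φ(0.045 × √(6 × 507 / 0.5816) − 1.960) = 0.902

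A common odds ratio of 0.62 (30% against 21% with any event) gives power 0.913. The stated effect of 0.64 fits these figures as an odds ratio, not as a log odds ratio.

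**3. If raised baselines were counted as MINS**

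Assume control-arm MINS rises from 20% to 60%. The protocol does not give the share already raised at randomisation, so this is an illustration. It can be reached in three ways:

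- **Equal addition.** The same 40 points move from rank 1 to rank 2 in each arm. This fits if patients with a raised baseline could not have had new MINS in any case.
- **Masking.** The same fraction of rank 1, 0.40/0.70 = 0.571, moves to rank 2 in each arm, and likewise from rank 4 to rank 5. This fits if baseline elevation is unrelated to later injury, so that some prevented events are hidden.
- **Effect carries over.** The relative effect also applies to the enlarged MINS rate.

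| MINS 60%, 507 per arm | Power, 30% RRR per component | Power, odds ratio 0.62 |
|---|---|---|
| As planned (MINS 20%) | 0.902 | 0.913 |
| Equal addition | 0.892 | 0.915 |
| Masking | 0.424 | 0.475 |
| Effect carries over | above 0.99 | 0.97 |

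For the first column, equal addition has θ = 0.551 and V = 0.774; masking has θ = 0.5279 and V = 0.756. At MINS 40% the first column gives 0.85 for equal addition and 0.62 for masking.

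**4. Weight of rank 2**

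MINS is 20 of 30 points of expected events (67%) when MACE includes death. If the 10% excluded death, it would be 20 of 37 (54%). It is the largest component either way.

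**The case against.** The strongest reply is that the primary outcome already has its own definition. Section 1.4.1 states what new MINS is, and every rank that uses MINS says new. Appendix A defines MINS without that word, in an appendix on complications. Section 7.1 collects new MINS and the Appendix A complications as separate 30-day items, and section 1.3.2 has a separate secondary outcome of any elevation. Appendix A may simply describe that broader outcome, and the entry in section 1.4.2 is only a line in a list.

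Most of this stands: section 1.4.1 is the more natural governing text. It does not settle the matter, for two reasons. Section 16.2 also restates the MACE components, so an adjudicator could fairly take it as endpoint text. And section 1.4.1 read alone still runs from surgery, does not tie newness to the randomisation sample, and does not name the URL.

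Two further replies also stand. The pre-operative gap is probably small, since the haemoglobin trigger is usually reached after surgery. And the detailed rule for raised baselines could properly sit in an adjudication charter, which is not shown.

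A reader might infer from the 20% and 60% figures that the appendix wording would halve the trial's power. The documents do not support that. The pilot figure covers any perioperative elevation, not elevation at randomisation, and the loss arises only under the masking assumption. With equal addition power hardly changes, and it rises if the effect carries over.

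**Conclusion.** This is an inconsistency in the primary endpoint and should be resolved. The three descriptions differ in newness, pattern, cause and clock, and none states how a troponin already raised at randomisation is handled. As written, rank 2 could include injury that preceded allocation or omit injury that followed it.

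That conclusion rests on the text and needs no power figure. The size is uncertain. On the assumption that MINS reaches 60%, power at 507 per arm is about 0.42 to 0.48 under masking, 0.89 to 0.91 under equal addition, and higher if the treatment effect extends to the added cases. The range rests on the 70/20/3/7 control distribution and on a baseline-raised share that the protocol does not report. It should be quoted as a range, and the lower end should not be presented as the expected result.

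**What to change.** Rewrite section 1.4.1 so that new MINS for the primary outcome is explicitly an endpoint definition that:

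- runs from randomisation, whether or not surgery has taken place;
- is judged against the central baseline troponin;
- has a pre-specified rule for participants whose baseline already exceeds the URL;
- names which URL from section 6.3 applies, overall or sex-specific.

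Then make section 1.4.2 and Appendix A 16.2 refer to the revised 1.4.1. Pointing them to the present text would only keep the surgery clock. Retain any-elevation myocardial injury as the separate secondary outcome named in section 1.3.2, and list it as such in 1.4.2.

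Settle this before adjudication and unblinding. The cost is protocol and charter wording only: the baseline and two later troponins are already collected and assayed centrally. The counted MINS rate may be somewhat lower under the stricter rule.
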